## 1 STUDY SUMMARY

## 1.1 Synopsis

## **Protocol title**

A Phase I Clinical Trial to Evaluate the Safety, Tolerability, and Pharmacokinetics of Single Ascending Doses of 4P-004 Versus Placebo Injected in the Target Knee Joint of Patients with Grade 2 to 4 Osteoarthritis on the Kellgren and Lawrence Severity Index (KL 2-4).

#### **Short title**

Safety, tolerability and pharmacokinetics of intra-articular (IA) single ascending dose of 4P-004 in patient with Kellgren and Lawrence grade 2 to 4 osteoarthritic (OA) knee.

#### Acronym

LASARE : safety, tolerabiLity, and phArmacokinetics of Single Ascending doses of 4P-004 versus placebo injected in the taRget knee joint of patients with grade 2 to 4 ostEoarthritic (OA) knee.

## **Objectives**

## Primary objectives

- To characterize safety and tolerability of single IA administration of 4P-004 at escalating doses in participants with knee OA.
- To determine the maximum tolerated dose (MTD) defined by occurrence of Dose Limiting Toxicities (DLTs)

## Secondary objective

• To characterize the plasma PK of liraglutide when administered as single IA doses at escalating dose levels in participants with knee OA.

#### **Exploratory Objectives**

• Collection of biological fluids (blood, urine)

#### **Endpoints**

#### **Primary Endpoints**

- Number of Adverse Events (AEs), serious AEs (SAEs) (Common Terminology Criteria Adverse Events [CTC-AE]) including target knee pain, and tenderness, erythema, swelling, local pain at injection site.
- Vital signs, ECG: Mean change, number of PCSA (Potentially Clinically Significant Abnormality), Percentage of participants with PCSA.
- Laboratory changes (RBC, WBC, ALT, AST, glycemia, amylasemia, creatinin clearance): Mean changes number of PCSA, Percentage of participants with PCSA.

## Secondary Endpoint

• Plasma concentration of liraglutide following a single IA injection. PK samples: pre-injection (T0-4h) and 2, 4, 8, 12, 16 and 24-hours post injection.

## Exploratory endpoints

Serum and Urine OA-related biomarkers (exploratory proteomic research of 4P-004 efficacy-related biomarkers).

#### Overall design

This phase I study is a multicenter, randomized, double-blind, placebo-controlled study to assess the safety and tolerability of single ascending dose of IA 4P-004 in participants,

- Between 18 and 80 years of age,
- with target knee OA stage KL 2-4

A total of 32 participants will be enrolled in 4 cohorts, in each cohort participants will receive either 4P-004 or placebo (6:2).

## **Description of Sites/Facilities Enrolling Participants**

Three investigational sites will participate.

Participants will be recruited via investigator's patient register or via advertising.

## **Description of study intervention**

4P-004 or placebo IA injection

## **Data and Safety Monitoring Board (DSMB)**

The DSMB will be composed of 2 independent physicians specialized, one in rheumatology and one in diabetology.

After each dose level completion (and at any time if needed), a DSMB evaluation based on a safety data analysis is intended by the sponsor before moving forward to the next higher dose level (or to randomize the next participant).

## **Study Duration**

The total duration of the study is approximately 7 months

#### **Participant Duration**

The total duration of the study will be around 5 to 6 weeks for each participant:

- Screening between 4 to 14 days before treatment (D-14 to D-4)
- Treatment period of 1 day (D1)
- Follow-up period of 28 days

## 1.2 Study flowcharts

## 1.2.1 Whole study flowchart

Study Period	SCR	R	DZ	F	U	EoS
Study Day (D)	D-7 D-14/D-4	D1* D2		D4 ±1d	D4 ±1d D8** ±2d	
Visit (V)/ Phone Call (PC)						
Number	V1	V2		PC1 V3		PC2
Informed consent	х					
Incl/excl criteria	х	х				
ECG	х	х				
Target knee X Ray***	х					
Medical history	х	х				
Prior & conc medication	х	x	x	х	Х	Х
Demographics	х					
Body Weight	х	х			Х	
Hospitalization		<	>			
Inclusion		Х				
Randomization		Х				
Diary distribution	х					
Diary Verification		х	x	х	х	х
Study treatment						
Knee IA injection		X				
Safety assessment						
Physical Exam	х	х	х		Х	
Vital Signs	х	х	x		Х	
AEs / SAEs / AESI		х	х	х	Х	Х
Target knee pain	х	х	x	Х	Х	Х
Local reaction		Х	х			
Blood PK		Х	х			
Clinical safety laboratory tests						
SARS-CoV-2 Rapid Antigen Test		(x)				
Hematology	х				Х	
Chemistry / Serology	х				Х	
Glycemia / Glucose meter	х	х			Х	
Urine Pregnancy test		x				
Exploratory analyses						
Blood Sample		X	х		Х	
Urine Sample		х	х		Х	

EoS: end-of-study, FU: follow-up, RDZ: randomization, SCR: screening

\*D1 is a full day hospital (approximately 24 hours), the participant is discharged on D2.

\*\*D8 Visit: to be performed at any time (before D8) in case of premature study discontinuation.

\*\*\*Target knee X Ray: to be done locally before D1, but not necessary if performed within the 6 previous months.

#### Clinical safety laboratory tests:

- Results of SARS-CoV-2 Rapid Antigen Test should be negative on D1 before definitive
  inclusion and randomization in the study (test to be performed if required according to
  standard practice on site),
- Urine Pregnancy test for WOCBP should be negative on D1 before definitive inclusion and randomization in the study,
- Results of RBC, Hemoglobin, WBC, Platelets, AST, ALT, Amylasemia, creatinine clearance should be obtained before D1 (sampling within 14 days before D1),
- Tests for Human Immunodeficiency Virus (HIV), hepatitis B virus [Hepatitis B surface Antigen (HBsAg)] and hepatitis C virus [Hepatitis C virus antibodies (HCV-Ab)] can be based on participant-reported medical history, available medical records, and the most recently available laboratory results for the participant (tests performed within the previous 12 months).

## 1.2.2 Visit 2 (randomization): D1-D2 study flowchart (24h hospitalization)

D1 / D2	T0 - 4h*	ТО	1h	2h	3h	4h	5h	6h	8h	10h	12h	16h	24h
Urine Pregnancy Test	Х												
SARS-CoV-2 Rapid Antigen Test	(x)												
Definitive inclusion	X												
Randomization**	X												
Physical Exam	X												Х
Bodyweight	X												
Veinous line	X	Χ	Χ	Х	Χ	Χ	Χ	Χ	Χ	Х	Χ	Χ	Х
IMP IA injection		Χ											
Vital signs	X		Χ	Х		Χ			Χ		Χ		Х
ECG	X										x***		
AEs / SAEs / AESI	X	Χ	Χ	Χ	Х	Х	Х	Х	Χ	Х	Х	Х	Х
Target knee pain	X		Χ	Х	X	X	Χ	Χ					Х
Local reaction			Χ	Х	X	X	Χ						Х
Glycemia	X			Χ		Χ			Х		Χ	Х	
Blood glucose meter	Х		Χ					Χ		Х			Х
Blood PK sample	X			Χ		Χ			Χ		Х	Х	X
Blood sample	Х								Χ				Х
Urine Sample	Х								Χ				Х

[figure not shown]
\*For practical reasons, all procedures planned before T0 (time of administration) can be done within 4 hours before T0.

AEs / SAEs / AESI reporting is continuous during the hospitalization

\*\*Randomization will be done before T0once results of the SARS-CoV-2 test (if required according to standard practice on site) and urine pregnancy test (if necessary) are available. All assessments after T0 must be carried out  $\pm$  10 minutes compared to the theoretical time. \*\*\* A time window of  $\pm$  2 hours for the ECG planned at T0 +12 is allowed

## 1.2.3 Global study scheme

## 2 INTRODUCTION

## 2.1 Background

Osteoarthritis (OA) has been defined as "a disorder involving movable joints characterized by cell stress and extracellular matrix degradation initiated by micro- and macro-injury that activates maladaptive repair responses including pro-inflammatory pathways of innate immunity. The disease manifests first as a molecular derangement (abnormal joint tissue metabolism) followed by anatomic, and/or physiologic derangements (characterized by cartilage degradation, bone remodeling, osteophyte formation, joint inflammation and loss of normal joint function), that can culminate in illness." (OARSI). The disease occurs when the dynamic equilibrium between the breakdown and repair of joint tissues becomes unbalanced, often in a situation where the mechanical loads applied exceed those that can be tolerated by the joint tissues.

OA is characterized by progressive cartilage loss, subchondral bone-remodeling, osteophyte formation and synovial inflammation, with resultant joint pain and increasing disability. OA can affect single and/or multiple peripheral joints such as knee, hip, and hand.

Globally prevalent cases of osteoarthritis increased (and disability induced by OA) by more than 110% in almost 30 years with 517 million of affected people (GBD et al., 2020; Long et al., 2022).

The current therapeutic arsenal of OA aims at alleviating pain and minimizing loss of physical function. To date, there is no structural-modifying drug to slow or revert the disease. More precisely, standard therapy is patient personalized and includes changes in lifestyle (nutrition, exercise, weight loss, physical therapy) and symptom-modifying medications (paracetamol, topical and/or oral non-steroidal anti-inflammatory drugs (NSAIDs), opioid analgesics, IA injections of corticosteroids, and hyaluronic acid although there is no consensus to consider the latter a standard therapy. Prosthetic replacement surgery is performed when OA symptoms are advanced, and pain is unmanageable.

Liraglutide is a biotechnology-derived peptide for which the mechanism of action relies on the glucagon-like peptide GLP-1 receptor (GLP-1 receptor or GLP-1R) thanks to its GLP-1 analogue structure. GLP-1R is involved in the control of blood sugar level by enhancing insulin secretion. Liraglutide was originally studied as an agent that stimulates insulin release from pancreatic beta cells following oral nutrient ingestion, or postprandially, as well as an agent slowing stomach emptying with an impact on body weight management. These biological activities are the basis of the clinical indications claimed for the marketed product Victoza® (SmPC provided in IB, Appendix I), Saxenda® and Xultophy® (in association with insulin degludec) currently authorized in more than 50 countries including the EU, USA, UK, Canada, Australia.

## Considering the following:

- (i) Recent studies reporting the impact of the GLP-1 GLP-1R axis stimulation in chondrocytes (Que et al., 2019; Meurot et al., 2022) and macrophages (Shiraishi et al., 2012),
- (iii) The current therapeutic arsenal of osteoarthritis aims at alleviating pain and minimizing loss of physical function without disease modifying action,

the sponsor has investigated the potential of liraglutide to treat OA.

Unlike the approved conditions of Victoza® as detailed in the SmPC (i.e., daily subcutaneous bolus administration of maximum 1.8 mg), the investigational medicinal product (IMP) 4P-004 is intended to be administered by IA injection once.

4P-004 is intended to prevent OA associated physiopathological degeneration ("Prevent structural damage" as per CPMP/EWP/784/97 Rev. 1 "Guideline on clinical investigation of medicinal products used in the treatment of osteoarthritis").

In the current Investigator's Brochure (IB), all IMP-related non-clinical and clinical data supporting the safety and efficacy of the following items are provided:

- The new route of administration,
- The dose regimen,
- The indication in OA.

#### PK Data

In human, after a single subcutaneous (SC) administration (current authorized route of administration) liraglutide is well absorbed from the injection site. Overall bioavailability following SC administration is estimated to be 55% in human. The distribution volume is low and close to plasma volume, which indicates that a high fraction of liraglutide is circulating in plasma. Liraglutide is extensively bound to plasma protein (>98%).

The mean clearance following subcutaneous administration of a single dose liraglutide is approximately 1.2 l/h with an elimination half-life of approximately 13 hours.

#### Renal impairment

No dose adjustment is required for patients with mild or moderate renal impairment. There is no therapeutic experience in patients with end-stage renal disease, and Victoza is therefore not recommended for use in these patients.

#### Hepatic impairment

No dose adjustment is recommended for patients with mild or moderate hepatic impairment. Victoza is not recommended for use in patients with severe hepatic impairment.

#### Interaction Data

In vitro, liraglutide has shown very low potential to be involved in pharmacokinetic interactions with other active substances related to cytochrome P450 and plasma protein binding.

The small delay of gastric emptying with liraglutide may influence absorption of concomitantly administered oral medicinal products. Interaction studies did not show any clinically relevant delay of absorption and therefore no dose adjustment is required.

#### Safety pharmacology

Safety pharmacology studies were performed in rats and dogs to evaluate any adverse effects on the central nervous system (CNS), the respiratory system, or the cardiovascular system during initial marketing authorization. A transient and mild increase in glycemia was observed in male and female

rats following anesthesia and IA administration of 300 µg of 4P-004 that was resolved at 24h. This transient and reversible effect on blood glucose was not observed after IA knee joints administration of 0.9 mg of 4P-004 in Beagle dogs.

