## 2.3 Risk / Benefit Assessment

The safety profile of 4P-004 is well known when administered subcutaneously (for long-term use) but no human data is available regarding the safety profile after IA injection.

As part of its preclinical data package, the sponsor intends to rely on previously published and assessed data of liraglutide containing authorized medicinal products (Victoza®, Saxenda®) to address systemic safety and toxicology of liraglutide. PK studies performed in dogs have shown very reproducibly that there is no more liraglutide after 24h in the articulation after IA injection in the knee-joint (see IB). A GLP extended single dose toxicity study of knee IA administration 4P-004 has been performed in rats. The product was well tolerated, no adverse signs of toxicity were observed up to the higher tested dose of 300 µg, which was determined as the No Observed Adverse Effect Level (NOAEL) dose of the study. Detailed presentation of the GLP-Toxicity study is available in the current IB.

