## 3.2 Endpoints

#### 3.2.1 Primary endpoints

- Number of Adverse events (AEs), serious AEs (SAEs) (Common Terminology Criteria Adverse Events [CTC-AE]) from ICF signature to D29, including target knee pain and tenderness, erythema, swelling, local pain at injection site.
- Vital signs from D-7 to D8, ECG from D-7 to D1: Mean change, number of Potentially Clinically Significant Abnormality (PCSA), Percentage of participants with PCSA
- Laboratory changes (Red Blood Cells (RBC), White Blood Cells (WBC), Hemoglobin (Hb), platelets, alanine transaminase (ALT), aspartate transaminase (AST), glycemia, amylasemia, creatinin clearance) from D-7 to D8: Mean changes number of PCSA, Percentage of participants with PCSA.

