### **Table TTT. Chemistry over Time**

### **Table TTT. Chemistry PCSA over Time**

Glycemia is measured as follows:

Visit	Timepoint	Method
Screening	-	Blood
Visit 2	Pre-Dose	Blood & Glucometer
Visit 2	1h Post-Dose	Glucometer
Visit 2	2h Post-Dose	Blood
Visit 2	4h Post-Dose	Blood
Visit 2	6h Post-Dose	Glucometer
Visit 2	8h Post-Dose	Blood
Visit 2	10h Post-Dose	Glucometer
Visit 2	12h Post-Dose	Blood
Visit 2	16h Post-Dose	Blood
Visit 2	24h Post-Dose	Glucometer
Visit 3	-	Blood & Glucometer

In order to obtain one value per scheduled timepoint:

- The baseline value will be selected as the last measure before IMP injection. If there are such two measures (same time, different method), then Blood will be selected.
- Post-baseline, if there are two measures for a scheduled timepoint, Blood will be selected.
- Additional samples vs. scheduled samples will not be analyzed, unless they are the baseline.

The values will be reported over time (Baseline, 1h Post-Dose to 24h Post-Dose) with the same template as Vital Signs.

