# 19 Potentially Clinically Significant Abnormalities

Potentially clinically significant abnormality (PCSA) values are defined as abnormal values considered medically important by the Sponsor, according to predefined criteria/thresholds based on literature reviews and defined by the Sponsor for clinical laboratory tests, vital signs, and ECG parameters.

When possible, PCSA will be computed at baseline or before.

Parameter	PCSA	Comments
Chemistry		
AST or ALT	> 3 ULN	Guidance for Industry Drug-Induced Liver Injury FDA, 2009
Potassium	< 3 mmol/L or ≥ 5.5 mmol/L	
CLcr (mL/min) (Estimated creatinine clearance based on the Cokcroft Gault equation)	< 15 (end stage renal disease) ≥ 15 - < 30 (severe decrease in GFR) ≥ 30 - < 60 (moderate decrease in GFR)	FDA draft Guidance 2020 Pharmacokinetics in Patients with Impaired Renal Function Study Design, Data Analysis, and Impact on Dosing
Amylasemia	≥ 1.5 ULN	
Glycemia	< 70 mg/dL	DSMB
Hematology		
RBC	≥ 6 Tera/L	
Hb	≤ 115 g/L (Male); ≤ 95 g/L (Female) ≥ 185 g/L (Male); ≥ 165 g/L (Female) Decrease from Baseline ≥ 20 g/L	Criteria based upon decrease from baseline are more relevant than based on absolute value.
WBC	< 3.0 Giga/L (Non-Black) < 2.0 Giga/L (Black) ≥ 16.0 Giga/L	
Lymphocytes	> 4.0 Giga/L	
Neutrophils	< 1.5 Giga/L (Non-Black); < 1.0 Giga/L (Black)	International Consensus meeting on drug- induced blood cytopenias, 1991. FDA criteria.
Monocytes	> 0.7 Giga/L	
Basophils	> 0.1 Giga/L	
Eosinophils	> 0.5 Giga/L	Harrison- Principles of internal Medicine 17th Ed., 2008
Platelets	< 100 Giga/L ≥ 700 Giga/L	International Consensus meeting on drug- induced blood cytopenias, 1991.
Vital Signs		
HR (bpm)	≤ 50 + decrease from baseline ≥ 20 ≥ 120 + increase from baseline ≥ 20	
SBP (mmHg)	≤ 95 + decrease from baseline ≥ 20 ≥ 160 + increase from baseline ≥ 20	
DBP (mmHg)	≤ 45 + decrease from baseline ≥ 10 ≥ 110 + increase from baseline ≥ 10	
ECG		
HR (bpm)	< 50 < 50 + decrease from baseline ≥ 20 > 100 > 100 + increase from baseline ≥ 20	
PR (ms)	> 200 > 200 + increase from baseline ≥ 25%	
QRS (ms)	> 110 > 110 + increase from baseline ≥ 25%	
QT (ms)	> 500

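### The glycemia PCSA flags only low values, so the PCSA part of the primary laboratory endpoint cannot register a rise in glucose

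*Protocol*

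**What the plan says.** **The IA glucose data.** Protocol 2.1 (Safety pharmacology) states: "A transient and mild increase in glycemia was observed in male and female". The animals were rats, dosed IA with 300 µg after anesthesia, and the rise was gone by 24 h. The section adds: "This transient and reversible effect on blood glucose was not observed after IA knee joints administration of 0.9 mg of 4P-004 in Beagle dogs". Protocol 2.3 says that "no human data is available regarding the safety profile after IA injection".

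**The endpoint.** Protocol 3.2.1 lists, among the laboratory variables, "glycemia, amylasemia, creatinin clearance) from D-7 to D8: Mean changes number of PCSA, Percentage of participants with PCSA". No direction is given for any variable. Protocol 10.1.4 leaves the PCSA criteria to the SAP and says that results meeting them will be listed and summarized.

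**The criterion.** SAP 19 has one line for glycemia: below 70 mg/dL, annotated DSMB in the comments column. It gives no upper limit and no rise-from-baseline criterion.

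**The table.** For glycemia, SAP 12.7 says: "The values will be reported over time (Baseline, 1h Post-Dose to 24h Post-Dose) with the same template as Vital Signs". In the blood pressure shell in SAP 12.5, that template gives the value, the change from baseline, one row per PCSA criterion and a residual row labelled No PCSA.

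**The concern.** The PCSA count and percentage turn individual values into a statement about participants. In a descriptive study with 6 active participants per dose and no significance tests, such flags carry much of the safety summary. Here they look in one direction, while the only glucose change that the protocol describes by this route went in the other. The other glucose-specific rules also look only downward: the stopping rule, the dose-limiting toxicity definition, the AESI list and the repeat-test rule.

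Entry requires normal glycemia (I13) and excludes diabetes (E11), so a marked rise during the study would be new and worth counting. As the plan stands, the report could show No PCSA for every participant at a dose where some had clear rises. A reader could take that row to mean that glucose was unremarkable in both directions.

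**Working it through.** The plan states no power, alpha or effect size, so it has no statistical figure to reproduce on this point. Its enrolment figure does reproduce: 4 cohorts × (6 + 2) = 32, with 4 × 6 = 24 active. SAP 9.3 adds a ninth participant to cohort 3, which makes 33. This does not affect the argument.

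**Step 1. Apply the rule.** A value is a PCSA if glycemia < 70 mg/dL, and otherwise No PCSA.

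- 60 and 69 mg/dL: PCSA.
- 70, 90, 140, 180, 200, 250 and 300 mg/dL: No PCSA.

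No value, however high, can leave the residual row.

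**Step 2. Count where this applies.** The post-dose glycemia timepoints in SAP 12.7 are 1, 2, 4, 6, 8, 10, 12, 16 and 24 h, which is 9. The D8 value enters the chemistry tables (7.2 and 7.2.1) under the same criterion.

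**Step 3. Add a high-side limit.** The documents give none, so the limits here are assumptions to show behavior, not proposals.

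| Assumed upper limit (mg/dL) | Values flagged high, of those in step 1 |
|---|---|
| 140 | 140, 180, 200, 250, 300 |
| 180 | 180, 200, 250, 300 |
| 200 | 200, 250, 300 |
| 250 | 250, 300 |

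The low flags (60 and 69) are the same in every row.

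**Step 4. See what the mean change retains.** Suppose one active participant rises by d at one timepoint and the others do not change. The mean change is d/6 in the cohort and d/24 over all active participants. The values of d are assumptions.

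| d (mg/dL) | Cohort mean change, d/6 | Pooled active mean change, d/24 |
|---|---|---|
| 50 | 8.3 | 2.1 |
| 110 | 18.3 | 4.6 |
| 160 | 26.7 | 6.7 |
| 210 | 35.0 | 8.8 |

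In each case, if nobody falls below 70 mg/dL, the cohort's PCSA row reads 0/6 and its No PCSA row 6/6 = 100.0%. The maximum change in the same table would equal d, so the rise is diluted in the mean but still visible in the range.

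**Step 5. Compare with the rest of SAP 19.** Potassium is two-sided ("< 3 mmol/L or ≥ 5.5 mmol/L"). So are hemoglobin, WBC, platelets, heart rate and systolic and diastolic blood pressure. AST/ALT, creatinine clearance, amylase, RBC, lymphocytes, neutrophils, monocytes, basophils, eosinophils, PR, QRS and QT each have limits on one side only. Two-sidedness is therefore not the table's general rule. The case for a high side rests on the reported IA rise and on an endpoint that states no direction.

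**The case against.** The strongest reply is that a low-side rule is a deliberate, risk-directed choice. Liraglutide lowers glucose, protocol 4.2 names its hypoglycemic properties as a risk to mitigate, and the glycemia limit carries a DSMB annotation. One-sided criteria are common in the same table. The rat effect was mild and transient, followed anesthesia and was absent in dogs, and protocol 2.3 takes 300 µg as the no-observed-adverse-effect level in rats. All of this stands. It explains why there is a low limit, but nothing in the documents says why there is no high one.

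A second reply is that a rise would be seen anyway. A reader might infer from the criterion that a glucose rise would go unrecorded, or survive only as a small shift in a mean. The documents do not support that:

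- SAP 9 and 12.5 give the minimum and maximum of the value and of the change from baseline.
- SAP 9 bases the safety evaluation partly on review of individual values, and Listing 16.2.16 covers glycemia.
- Protocol 8.1.4 and 11.3.1 make a clinically significant laboratory change an adverse event in either direction, and adverse events are themselves a primary endpoint.

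What remains is narrower. These routes depend on inspection or investigator judgement, and none applies a threshold fixed in advance.

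A third reply concerns interpretation. Protocol 8.5.2 has sugar given for symptoms that include nausea. If nausea is more frequent on active drug, sugar-related high values may be too, and comparison with pooled placebo (4 × 2 = 8 planned) would not remove that. The fasting state of the D1 samples is not specified. This limits how high flags can be read, but they can still be reported.

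**Conclusion.** The gap is real but limited. Two of the three glycemia components of the primary laboratory endpoint, the PCSA count and percentage, cannot register an increase at any of the 9 post-dose timepoints or at D8. The third, mean change, can register it but dilutes it: one participant rising by 50 to 210 mg/dL moves a six-person mean by 8.3 to 35.0 mg/dL. Those rises are illustrative. The documents give no size for the rat effect beyond calling it mild.

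A reader might go further and infer that the trial should expect hyperglycemia, or that a rise is the main effect of the product by this route. Neither is supported. The signal comes from one species, after anesthesia, with a negative result in dogs. In participants, protocol 2.3 reports nausea and vomiting in cohort 3 on blinded review.

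The conclusion rests on reading SAP 19 as the complete list of glycemia criteria. Further detail on the rat result may lie in the investigator's brochure, which was not available. This is a cheap improvement to reporting, not a defect that undermines the safety evaluation.

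**What to change.** - In SAP 19, add a high-side or rise-from-baseline glycemia PCSA category, for reporting only. Otherwise state why none is needed.
- Have blinded sponsor staff choose and justify the limit before unblinding, because the DSMB may see unblinded data (protocol 6.3). The limit must suit samples whose fasting state is not specified.
- In Tables 7.2.1 and 7.3, show low and high PCSA as separate rows, by dose and for pooled placebo.
- Mark high values recorded after sugar was given for symptoms.

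The glucose values are already collected, so the cost is one criterion line, an extra row in two tables and a marker. Study conduct and clinical rules do not change. The downside is that some high flags will reflect meals or sugar, possibly more often on active drug, so the accompanying text should call for cautious reading.
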